10.4.3 Analysis of the Secondary Endpoint(s)

Analysis of secondary efficacy endpoints will proceed in a similar fashion to the primary endpoints:

Goal attainment will be assessed at baseline and 3 months. At baseline, participants will set 1 personal goal related to improving daily function or symptom control (e.g., walking with less dyspnea, attending family functions). At 3 months, goal attainment will be rated using a 5-point GAS, scored as follows: no change from baseline (-2); less than expected (-1), expected (0), better than expected (+1), and much better than expected (+2). To preserve the ordinal nature of the data, we will calculate a median GAS score (-2 to +2) for each participant, and then compare the treatment and control groups using a Wilcoxon-Mann-Whitney rank-sum test.⁸⁹ Secondly, we will transform each participant’s GAS score into a single aggregated T-score using the standardized formula: $T = 50 + ([10\sum(w_i x_i)] / [(1-\rho)(\sum w_i)^2 + \rho(\sum w_i)^2]^{1/2})$, where w_i = weight assigned to the goal; x_i = the attained score for the goal (-2 to +2); and ρ = the expected correlation of the goal scales, commonly estimated to be 0.3. For this study, all weights will be assigned a value of 1 (i.e., all goals are weighted equally). A T-score of 50 indicates that on average the expected level of goal attainment was achieved.¹² We will then compare mean T-scores for treatment and control groups at 3 months using a two-sample t-test. We will also compare the percentage of participants in the treatment and control groups who met their expected level of goal attainment on at least 1 goal using a chi-square test.

Health status at 3 months will be assessed using linear regression with adjustment for baseline levels and a binary treatment indicator; if necessary, health status scores will be log-transformed to improve the approximation to normality. Activities of daily living (BADLs and IADLs) will be assessed using longitudinal models for interval scores, with indicators to incorporate time, a binary indicator of treatment group, and patient-level random effects to accommodate repeated assessments within individuals; if interval scores are not approximately normally distributed, suitable transformations will be sought. Hospital readmission and death will be evaluated using Kaplan-Meier estimates and tested with logrank statistics, as well as investigated using Cox proportional hazard models with adjustment for confounders if necessary. As with the models for the primary outcome, in each model described we will assess the need for adjustment for confounders using the change-in-estimate criterion.

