10.4.2 Analysis of the Primary Efficacy Endpoint(s)

6MWD

We will assess the difference in 6MWD by calculating difference scores for each participant and comparing the intervention and usual care groups with an independent group t-tests allowing for unequal variances. We will also regress 3-month 6MWD on a binary indicator of treatment group, with adjustment for baseline 6MWD and the stratification factor (enrollment site). While randomization should obviate the need for additional adjustment, we will explore whether adjustment for participant-level characteristics (e.g., demographic factors or referral to ambulatory CR) is necessary, using the change-in-estimate criterion. We realize that engagement with the mHealth-CR program may also affect attendance and engagement with structured ambulatory CR programs. We intend to explore this as a mediator of the effect of assignment to the intervention arm. We will use structural equation models to estimate the direct and indirect effects of mHealth, where the direct effect is that of mHealth-CR on the 6MWD, and the indirect effect is mediated through attendance at structured ambulatory CR.

Engagement

We hypothesize that (1) among participants offered mHealth-CR, there will be distinct trajectories of engagement (e.g., sustained engagement, disengagement, reengagement, deteriorating engagement); and (2) there will be significant differences in participant characteristics among these groups. While our aim is largely exploratory (given the paucity of data on mHealth-CR engagement), we will test whether the following characteristics are significant: age (≥ 80 years), sex, race/ethnicity, comorbidity burden (≥ 2 chronic medical conditions), frailty, social support (based on living alone), cognitive impairment (based on Mini-Cog), and depressive symptoms (based on PHQ-8). We selected these factors based on literature related to engagement in other technologies. We will conduct latent class analysis to identify profiles of engagement and explore whether these factors indicate membership in a class; these models use maximum likelihood estimation,

CONFIDENTIAL

This material is the property of the NYU School of Medicine and Langone Medical Center. Do not disclose or use except as authorized in writing by the study sponsor

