10.6 Measures to Minimize Bias

10.6.1 Enrollment/Randomization/Masking Procedures

Randomization. After providing informed consent and completing the baseline assessment, enrolled participants will be randomized by REDCap in a 3:1 ratio to either intervention (mHealth-CR) or control (usual care). The rationale for 3:1 randomization is to efficiently address both the primary comparison of mHealth-CR and usual care with respect to the 6MWD and to allow an adequate sample size to estimate engagement trajectories. The proposed 3:1 randomization enables a 50% increase in the sample size, while also providing excellent power for the primary hypothesis test. Randomization will be stratified by hospital (NYU-main campus, NYU Winthrop, Bellevue, UMMHC, Yale New Haven) to ensure balance across treatment arms given between-hospital population differences. The randomization code will be created by an independent biostatistician, and given to a DataCore staff member, with a backup copy retained by the independent biostatistician.

Missing data. In general, all available data will be included in data listings and tabulations. Population denominators will be displayed in column headers. Individual denominators will be displayed for each summary such that the amount of missing values will be evident. Patients who withdraw from the study or are lost to follow-up will still be included in the denominators for any proportions where data are available.

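### Randomization is stratified by hospital, but no secondary analysis in section 10.4.3 prespecifies hospital; if hospital is prognostic, the reported standard errors of the linear and rank-type comparisons are somewhat too large

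*Combined protocol and SAP*

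**What the plan says.** Section 10.6.1 states "Randomization will be stratified by hospital" and gives the reason: "to ensure balance across treatment arms given between-hospital population differences". Section 10.4.2 lists two primary efficacy analyses. The first is an unequal-variance t-test on change scores, with no site term. The second is a regression of 3-month 6MWD on arm, "with adjustment for baseline 6MWD and the stratification factor (enrollment site").

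Section 10.4.3 opens with a general sentence, "Analysis of secondary efficacy endpoints will proceed in a similar fashion to the primary endpoints", and then names the analyses one by one:

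- **GAS score:** "compare the treatment and control groups using a Wilcoxon-Mann-Whitney rank-sum test".
- **GAS T-score:** "compare mean T-scores for treatment and control groups at 3 months using a two-sample t-test". A chi-square test compares the proportions meeting their goal.
- **Health status:** "Health status at 3 months will be assessed using linear regression with adjustment for baseline levels and a binary treatment indicator".
- **ADLs:** a longitudinal model with time, arm and patient random effects.
- **Readmission and death:** "Hospital readmission and death will be evaluated using Kaplan-Meier estimates and tested with logrank statistics", plus Cox models with optional confounder adjustment.

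The section closes by saying that the need to adjust each model for confounders will be judged by a change-in-estimate rule. Hospital is not named anywhere in the section.

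**The concern.** The sponsor stratified because hospitals are expected to differ. Stratification makes the arms nearly balanced within each hospital, so hospital differences largely cancel out of the treatment contrast. An analysis without hospital still counts those differences as residual noise. Its standard error then describes a less precise design than the one actually run.

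At stake are interval width and power for secondary endpoints that have little to spare: the table in section 10.5 gives 73% for GAS, 67% at the low end for residual angina and 64% at the low end for ADLs. Leaving hospital unspecified also allows a choice between adjusted and unadjusted results after the data are seen, for tests that section 10.5 reports without multiplicity correction.

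**Working it through.** **Inputs from section 10.5.** 240 intervention and 80 usual care evaluable; two-sided 0.05; SF-12 difference 5, SD 12, power 90%; GAS difference 5, SD 15, power 73%.

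**Assumption.** ICC is the share of outcome variance lying between hospitals. The documents give no value, so the range 0 to 0.10 is shown.

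**Step 1: reproduce the stated power.** SE = SD × √(1/80 + 1/240) = SD × 0.1291.

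- SF-12: SE = 1.549; 5/1.549 − 1.96 = 1.268; power Φ(1.268) = 89.8% (stated 90%).
- GAS: SE = 1.936; 5/1.936 − 1.96 = 0.622; power Φ(0.622) = 73.3% (stated 73%).

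**Step 2: put hospital in the model.** The residual SD is multiplied by f = √(1 − ICC). Adjusted power is Φ(5/(f × SE) − 1.96). The SF-12 95% half-width is 1.96 × f × 1.549.

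| ICC | f | SF-12 half-width | SF-12 power | GAS power |
|---|---|---|---|---|
| 0 | 1.000 | 3.04 | 89.8% | 73.3% |
| 0.01 | 0.995 | 3.02 | 90.0% | 73.7% |
| 0.02 | 0.990 | 3.01 | 90.3% | 74.2% |
| 0.05 | 0.975 | 2.96 | 91.2% | 75.5% |
| 0.10 | 0.949 | 2.88 | 92.5% | 77.7% |

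Intervals narrow by 1 − f: 0.5% at ICC 0.01 and 5.1% at 0.10.

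**Step 3: compare with the unadjusted test under the same design.** Stratification already shrinks the true spread of the unadjusted estimate to about f × SE, while its reported error stays at SE. Its power is therefore Φ((5/SE − 1.96)/f), slightly above the plan's figure.

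- ICC 0.05: SF-12 Φ(1.268/0.975) = 90.3%, against 91.2% adjusted; GAS Φ(0.622/0.975) = 73.8%, against 75.5%.
- ICC 0.10: SF-12 Φ(1.268/0.949) = 90.9%, against 92.5%; GAS Φ(0.622/0.949) = 74.4%, against 77.7%.

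Measured this way, adjustment gains about 1 to 3 percentage points at these two values.

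**Step 4: simulation.** 6,000 trials per setting; hospitals of 100/100/150/50 (section 4.1 targets, with an equal split of the 200 NYU participants assumed); 3:1 blocks of four assumed; 20% dropout; SF-12 values; regression without and with hospital. The Monte Carlo error of the type I rates is about 0.3 points.

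| ICC | Mean reported SE | Power | Type I error |
|---|---|---|---|
| 0 | 1.55 / 1.55 | 89.7% / 89.7% | 5.0% / 5.0% |
| 0.05 | 1.55 / 1.51 | 89.6% / 90.6% | 4.4% / 5.0% |
| 0.10 | 1.55 / 1.47 | 90.7% / 92.8% | 4.3% / 5.1% |

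(Each cell: without / with hospital.) At ICC 0.02 no conservatism was visible (type I error 5.4% without hospital). At ICC 0.10 the unadjusted estimates had an actual spread of 1.47 to 1.50 against a reported 1.55. The fault lies in the reported error, not the estimate.

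**Step 5: time to event.** 400 simulated trials with assumed hospital hazard multipliers of 0.6 to 2.0 and a true hazard ratio of 0.55. The SE of the log hazard ratio was 0.223 unstratified and 0.223 stratified; power was 71% and 72%. The mean log hazard ratio moved from −0.565 to −0.580 (hazard ratio 0.568 to 0.560). Stratifying moved the ratio slightly away from 1 and left the interval width unchanged.

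**Step 6: would the change-in-estimate clause bring hospital in?** It looks for covariates that move the treatment estimate. With 3:1 allocation inside every hospital, hospital is nearly uncorrelated with arm, so adding it lowers residual variance but hardly moves the estimate. The screen would usually drop it. As written, the clause reaches models only, not the rank-sum, t-, chi-square or logrank tests. Section 10.4.2 itself treats site as a fixed covariate and uses this rule only for adjustment beyond it.

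**The case against.** The strongest reply is that the plan does not rule hospital out. The lead-in ("Analysis of secondary efficacy endpoints will proceed in a similar fashion to the primary endpoints") can be read as carrying the primary regression's site term across, and the closing clause allows adjustment of each model. This stands to a degree: in the linear, mixed and Cox models hospital is unspecified, not excluded. But the lead-in is ambiguous, because one of the two primary analyses has a site term and the other does not. The covariates listed for health status carry over baseline and omit site, and a rank-sum or chi-square test as named has no place for a stratum.

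The first-listed primary t-test also omits site, so an unadjusted GAS t-test fits the plan's own pattern. That is true, and the contrast with the primary endpoint should be drawn with its regression only.

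A reader might infer that the secondary estimates lose precision. They lose little, since stratification already protects them; it is the reported error that is too large. A reader might also infer that the readmission interval is too wide. Step 5 does not support this: the marginal and within-hospital hazard ratios are different quantities, and choosing between them is partly a matter of preference.

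Finally, adjustment is not wholly free of difficulty. Bellevue's target of 50 gives about 12 controls, or about 10 after 20% dropout. Section 10.6.1 lists Yale as a stratum while section 4.1 says enrollment there is paused, so a very small stratum is possible. This stands, and the fix has to deal with it.

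**Conclusion.** The point holds as a low-cost improvement to the secondary analyses. None of them prespecifies the randomization stratum, and the adjustment clause would not reliably supply it. If hospital is prognostic, the linear and rank-type comparisons report standard errors that are too large, and their tests are slightly conservative.

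The size depends on an assumed 1-10% of outcome variance lying between hospitals: intervals about 0.5-5% narrower, GAS power about 74-78% and SF-12 power about 90-92.5% when set against the plan's own 73% and 90%. Against an unadjusted test in the same stratified design the gain is smaller (step 3). It is nil if hospital explains nothing, and for health status the baseline adjustment may already absorb part of it.

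A reader might go further and conclude that the secondary tests are invalid or the power table wrong. Neither follows. The error is on the conservative side, and the SF-12 and GAS power figures reproduce.

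**What to change.** In section 10.4.3, state that hospital, as used in the randomization, enters as follows:

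- **Health status and ADLs:** a fixed term in the models.
- **GAS:** the van Elteren (stratified rank-sum) test for the score; a linear model with arm and hospital in place of the T-score t-test; Cochran-Mantel-Haenszel for proportions.
- **Readmission:** a hospital-stratified logrank test and Cox model, with the hazard ratio described as a within-hospital one.
- **Death:** descriptive, in line with section 4.2.2, which does not expect a significant difference.
- **Sparse strata:** a pooling rule fixed before outcomes are seen, covering Yale in particular.

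The cost is a paragraph of wording. Hospital is already recorded for the randomization, and no extra data or participants are needed.

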4.2.2 Secondary Study Endpoints

Protocol-defined secondary endpoints are: (1) goal attainment, as measured by goal attainment scaling (GAS); (2) change in participant reported health status: general (SF-12) and disease specific (SAQ-7); (3) change in activities of daily living (ADLs); (4) hospital readmission; and (5) death, in participants receiving mHealth-CR versus usual care.

- *Goal attainment*, defined as whether a person's individual functional goals are achieved as a result of the study intervention, will be measured using a 5-point goal attainment scale (GAS). Using the SMART goal framework,⁶³ GAS describes the person's expected level of goal achievement over 3 months, ranging from no change (scored as -2) to much better than expected (scored as +2). Scales are dynamically set according to a person's needs, while measurement of attainment is standardized. Goal attainment, through goal setting, is an especially important outcome in older adults who may begin an intervention with a variety of deficits (therefore necessitating individualized therapy towards realistic goals).⁶⁴
- *Participant reported health status* is measured using the SF-12⁶⁵ (general health status) and Seattle Angina Questionnaire 7 (SAQ-7)⁶⁶ (disease-specific health status). Health status encompasses a person's functional status, symptoms, and well-being, and is increasingly recognized as an important patient-centered outcome.^{67,68} Both the SF-12 and SAQ-7 have been validated and are convenient for participants (<5 minutes to administer). For the SF-12, we will analyze change from baseline to 3 months using a threshold of 5 points in SF-12 physical component score (PCS) as a clinically meaningful change.⁶⁹ For SAQ-7, we will analyze at a single time point (3 months) the number of participants who have residual angina (SAQ-7<100) vs. no angina (SAQ-7=100).⁶⁶
- *Change in ADLs* is defined as any improvement or worsening in basic (BADLs) or instrumental (IADLs) activities of daily living over 3 months. BADLs are basic self-care behaviors: feeding, toileting, bathing, dressing, and ambulating.⁷⁰ IADLs are activities that allow a person to live independently (e.g. food preparation, medication management, transportation, shopping, managing finances, using the telephone, and housekeeping).⁷⁰ ADL preservation is repeatedly cited by older adults as an important outcome,⁹ and prior research has shown that many patients with IHD experience ADL decline after hospitalization.⁷¹

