10.2 Statistical Hypotheses

Primary Endpoints

Efficacy: 6 minute walk distance (6MWD)

Hypothesis: Degree of improvement in 6MWD will be greater in participants assigned to mHealth-CR than in those assigned to usual care.

Engagement: Mobile health (mHealth) use

CONFIDENTIAL

This material is the property of the NYU School of Medicine and Langone Medical Center. Do not disclose or use except as authorized in writing by the study sponsor

Hypotheses: (1) Among participants offered mHealth-CR, there will be distinct trajectories of engagement (e.g., sustained engagement, disengagement, reengagement, deteriorating engagement); and (2) there will be significant differences in participant characteristics among these groups.

Secondary Endpoints

1. Goal attainment (measured by Goal Attainment Scaling)
2. Health status (measured by SF-12 and SAQ)
3. Activities of daily living (ADLs)
4. Hospital readmission
5. Death

Hypotheses: Goal attainment scaling, health status, and ADLs will improve in participants who are offered mHealth-CR compared with usual care. Hospital readmission and death will be lower in participants who are offered mHealth-CR compared with usual care.

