with our expected sample of 320 patients, using two-sided, 0.05-level tests; we will not implement multiple comparisons correction for these secondary outcomes. Baseline event rates and standard deviations are estimated from the literature.¹¹⁵⁻¹¹⁸ For example, we have 90% power to detect a difference between groups of 5 units in the SF-12 score.

All comparisons between the randomized groups in this trial will be performed according to the principle of "intention-to-treat"; that is, participants will be analyzed according to the treatment group to which they were randomized, regardless of subsequent crossover. The intent-to-treat (ITT) population will include all subjects who receive a randomized treatment assignment, except for those with a documented violation of trial eligibility criteria.

The table below shows clinically meaningful effect sizes for secondary efficacy outcomes, and gives the power to detect these effect sizes with our expected sample of 320 patients, using two-sided, 0.05-level tests; we will not implement multiple comparisons correction for these secondary outcomes.

Outcome	Endpoint definition	Effect size	Estimated s.d.	Power
Goal attainment scaling	GAS score	5	15	73%
Health status	SF-12	5	12	90%
Health status	Residual angina on SAQ	15-20%	n/a	67-93%
ADLs	Standardized ADL score	15-20%	1	64-87%
Hospital readmission	Admission by 3 months	15%	n/a	91%
Death	Death by 3 months	10%	n/a	82%

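### SAQ-7 is defined and powered as a binary 3-month endpoint, but Section 10.4.3 prescribes only a regression of health-status scores, which estimates something else

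*Combined protocol and SAP*

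**What the plan says.** - **Definition (4.2.2).** The time frame is fixed: "For SAQ-7, we will analyze at a single time point (3 months". The outcome is a count: "the number of participants who have residual angina (SAQ-7<100) vs. no angina (SAQ-7=100". The list that opens the same section labels the item differently, as "change in participant reported health status: general (SF-12) and disease specific (SAQ-7".
- **Grouping (10.2).** The second secondary endpoint is "Health status (measured by SF-12 and SAQ", so the SAQ falls under that heading.
- **Power (10.5, table).** The row "Residual angina on SAQ" has an effect size of 15-20%, a standard deviation of n/a and power of 67-93%. The assumed control rate is not given.
- **Analysis (10.4.3).** One method is given for the heading: "Health status at 3 months will be assessed using linear regression with adjustment for baseline levels and a binary treatment indicator". The fallback is "if necessary, health status scores will be log-transformed to improve the approximation to normality".

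No section names a test or model for the binary SAQ-7 outcome.

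**The concern.** An analyst who follows Section 10.4.3 literally would regress the 3-month SAQ-7 score on treatment and baseline score and report a mean difference. Section 4.2.2 promises a comparison of how many participants still have angina, and the power table refers to that comparison. These are different estimands and need not agree in size or in conclusion. The reported result would then not answer the stated endpoint, and the 67-93% would be attached to an analysis it was not calculated for.

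The fallback adds a second problem. Section 4.2.2 makes 100 the no-angina value and everything below it residual angina, so the score has a ceiling. A log-transform does not remove a ceiling. It also stretches the lower tail, which is the wrong direction for a left-skewed score.

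**Working it through.** **1. Which kind of calculation lies behind each row of the 10.5 table?** Inputs from 10.5: 80 usual care, 240 intervention, two-sided 0.05.

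For means, power = Φ(δ/σ × √(n₁n₂/(n₁+n₂)) − 1.96), with √(80×240/320) = √60 = 7.746.

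- SF-12 (δ 5, σ 12): 0.4167 × 7.746 = 3.227; Φ(1.267) = 89.8%. The table says 90%.
- GAS (δ 5, σ 15): 0.3333 × 7.746 = 2.582; Φ(0.622) = 73.3%. The table says 73%.

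The score rows reproduce as two-means power. The SAQ row has no standard deviation and cannot come from that formula.

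For proportions (pooled test), power = Φ((d − 1.96·SE₀)/SE₁), where SE₀ = √(p̄(1−p̄)/60) and SE₁ = √(p₁(1−p₁)/80 + p₂(1−p₂)/240). The control rate is unstated, so it has to be assumed; the effect is read as an absolute reduction, also an assumption. At a control rate of 0.45:

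- d = 0.15: p̄ = 0.3375, SE₀ = 0.0610, SE₁ = 0.0630; Φ(0.48) = about 69%.
- d = 0.20: p̄ = 0.30, SE₀ = 0.0592, SE₁ = 0.0622; Φ(1.35) = about 91%.

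Sensitivity to the assumed control rate:

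| Control rate | d = 0.15 | d = 0.20 |
|---|---|---|
| 0.30 | 82% | 98% |
| 0.40 | 72% | 93% |
| 0.50 | 66% | 90% |
| 0.60 | 64% | 88% |

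The stated 67-93% cannot be reproduced strictly, but it is compatible with a two-proportion test. Both ends come within 2 points at control rates of about 0.38-0.45, depending on the test variant; a continuity-corrected test also fits at 0.815.

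**2. Do the two analyses estimate the same thing?** Let p be the proportion below 100 and m the mean score among those participants. The arm mean is 100 − (100 − m)p. Assume 40% residual angina in control and 25% in intervention, with m = 75 in control. The control mean is 100 − 25 × 0.40 = 90.

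| m, intervention | Intervention mean | Mean difference | Fall in residual angina |
|---|---|---|---|
| 85 | 100 − 15 × 0.25 = 96.25 | 6.25 | 15 points |
| 75 | 100 − 25 × 0.25 = 93.75 | 3.75 | 15 points |
| 60 | 100 − 40 × 0.25 = 90.00 | 0 | 15 points |

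The defined endpoint is identical in all three rows; the regression target is not.

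**3. What does the log do?** A 10-point step just below the cap becomes ln(100/90) = 0.105; the same step from 50 to 40 becomes ln(50/40) = 0.223. The lower tail is stretched, and every score of 100 stays at one value. In simulation with assumed distributions, skewness went from about −1.6 to −1.9, and the power of the baseline-adjusted score regression fell by about 4-6 points compared with the untransformed score.

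**4. Does the score regression have less power than the binary test?** With 60% of control and 75% of intervention assumed at 100, an unadjusted score test had 56.1% power in one simulation, against about 70% for the binary test. But 10.4.3 adjusts for baseline. The implied z is 1.96 + Φ⁻¹(0.561) = 2.11; dividing by √(1−ρ²) gives:

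- ρ = 0.4: 2.31, power 64%
- ρ = 0.5: 2.44, power 68%
- ρ = 0.6: 2.64, power 75%

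A separate simulation gave 72% for the binary test. The adjusted score regression had 59-71% for assumed latent correlations of 0 to 0.6, and 87% once a 5-point benefit below the cap was assumed. The order therefore changes with quantities that the plan does not state.

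**The case against.** The strongest reply is that the endpoint is already fixed in advance (instrument, cut-point and time point in 4.2.2), that the synopsis promises a test suited to continuous or categorical measures, and that 10.4.3 never names SAQ-7. On that view only the name of a test is missing. Part of this stands: the endpoint definition is not open, and the link from 10.4.3 to SAQ-7 runs through 10.2. But the synopsis line names no test. Where 10.4.3 intends a categorical analysis it says so, as with the chi-square test for goal attainment; SAQ-7 receives nothing of the kind.

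A second reply is that linear regression of a 0/1 indicator estimates a risk difference. The text does not fit that reading: it refers to scores, and the log of a 0/1 variable is undefined at 0.

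A reader might also infer more than the documents support:

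- **That the score regression loses power.** An unadjusted comparison suggests it, but omits the baseline adjustment that 10.4.3 prescribes and depends on an assumed score distribution.
- **That the log-transform is bound to be used.** The clause is conditional and sets no criterion. Control rates near 0.38-0.45 would put more than half of participants at 100, but those rates are back-solved, and 0.815 also fits one test variant.
- **That the SF-12 analysis is wrong too.** Linear regression suits SF-12. In an illustrative simulation the log changed its power only from 90.9% to 89.4%, and nothing in the documents calls for robust standard errors. What remains is interpretability: a log-scale effect cannot be read against the 5-point PCS threshold.

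**Conclusion.** The mismatch holds, and it rests on the text: SAQ-7 is binary in 4.2.2 and in the 10.5 table, while the only health-status analysis in 10.4.3 is a score regression. Followed as written, 10.4.3 estimates a different quantity from the one defined and powered, and the 67-93% does not describe it. The illustration of 0 to 6.25 points for one 15-point fall in residual angina shows that the two can disagree; its inputs are assumed.

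No power penalty is established in either direction. The log clause is unsuitable for SAQ-7 because of the ceiling, and it makes left skew worse if many participants are at the cap; the plan does not say how many will be.

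The reach is limited to one component of one secondary endpoint, for which 10.5 plans no multiplicity correction. The primary analysis and the sample size are unaffected. The correction should be made before outcome data are analysed.

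**What to change.** Amend Section 10.4.3:

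1. Analyse SAQ-7 below 100 at 3 months with a binary model, for example logistic regression on treatment, baseline SAQ-7 and site. Site is the stratification factor and is already in the 6MWD regression in 10.4.2.
2. Report a standardised (marginal) risk difference with 95% CI. A logistic coefficient is an odds ratio, so the text should say that each participant's predicted risk is averaged under each assignment and the two averages are subtracted.
3. Label any SAQ-7 score analysis supportive, and do not log-transform SAQ-7.
4. Keep linear regression for SF-12 PCS and report it on the original scale, so that it can be read against the 5-point threshold.

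It would also help to align the label in the 4.2.2 list, which calls SAQ-7 a change, with the single-time-point definition, and to state the assumed control rate in 10.5.

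The cost is SAP wording only: no new data, visits or participants. The 67-93% can stay, since it is already presented for a percentage outcome.
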